3.0 Objectives

3.1 Primary Objectives

- 3.1.1 To assess whether treatment with IMPT results in longer time to cognitive failure compared with IMRT. Cognitive failure is defined as the first cognitive failure on any of the following six cognitive outcome variables: Hopkins Verbal Learning Test Revised (HVLT-R) Total Recall, HVLT-R Delayed Recall, HVLT-R Delayed Recognition, Controlled Oral Word Association (COWA), Trail Making Test (TMT) Part A or Part B.
- 3.2 Secondary Objectives
 - 3.2.1 To determine local control in the brain post radiation treatment.
 - 3.2.2 To determine overall survival in each treatment arm.
 - 3.2.3 To assess quality of life measured at two month intervals for a total of two years post-radiotherapy for both treatment arms.
 - 3.2.4 To assess the pattern of cognitive change in memory at two month intervals for two years post-treatment as well as executive function and processing speed.
 - 3.2.5 MRI diffusion weighted images (DWI) and reconstructed apparent diffusion coefficient (ADC) maps will be analyzed to see if there is a difference between pre- and post-treatment scans. These will also be analyzed for differences between the two treatment modalities.
 - 3.2.6 To evaluate if diffusion tensor imaging (DTI) correlates to the cognitive changes and if there are differences between the two treatment modalities.
 - 3.2.7 To assess the pre-treatment factors of recursive partitioning analysis (RPA) class and mini mental status examination (MMSE) in the predictive determination of local and distant control and cognitive outcome in each treatment arm.
 - 3.2.8 To assess the correlation between location of primary lesion, total volume of intracranial disease, and cognitive outcome in each treatment arm.
 - 3.2.9 To determine the relationship between MGMT promoter methylation status and cognitive and local control outcomes.
 - 3.2.10 To document and descriptively compare post-treatment adverse side effects between the two treatment arms.
 - 3.2.11 To determine the relation between dosimetric parameters and cognitive and local control outcomes.
- 3.3 Correlative objectives
 - 3.3.1 To determine if Apo E (i.e., Apo E2, Apo E3, and Apo E4) genotyping may prove to be a predictor of radiation induced neurocognitive decline (or neuro-protection).
 - 3.3.2 To determine if inflammatory markers (i.e., IL-1, IL-6, and TNF- α) may prove to be predictors of radiation induced neurocognitive decline.

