7.0 Treatment Plan

- 7.1 Eligible patients will be randomized in equal numbers to each treatment arm using CORe. Randomization will be stratified using the following factors:7.1.1 RPA class (III or IV vs. V)
 - 7.1.2 Mini Mental Status Examination score (21-26 vs. 27-30)
 - 7.1.3 Age (less than 65 vs. 65 or older)
- 7.2 Following randomization, insurance pre-authorization will be obtained for the specified treatment modality. If a patient's insurance will not cover payment for the assigned treatment arm, that patient will be removed from the study and will be treated off protocol.
- 7.3 Radiation target definition for glioblastoma as follows. GTV defined as tumor cavity and any T1 tumor enhancement. CTV will include GTV + 2 cm margin customized to include FLAIR enhancement (if thought by the radiation oncologist to be tumor) and exclude bone, fascia, and other anatomical barriers. PTV-50 will include CTV + 3-5 mm and will be treated to 50 Gy in 30 fractions. PTV-60 boost volume will include GTV + 3-5 mm and will be treated to 60 Gy in 30 fractions.
- 7.4 For patients randomized to IMRT, treatment will be planned using Pinnacle software system. Planning will be based on non contrast CT images obtained at time of simulation in addition to MRI scan. Treatment will be delivered using linear accelerator. Fractionated radiation will be delivered daily M-F with weekends off for all patients. IMRT plans use a configuration of five to seven isocentric 6-MV photon beams delivered in a step-and-shoot technique. For inverse planning specified dose constraints are given to organs at risk including the brainstem, spinal cord, optic chiasm, optic nerves, and cochlea.

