- 10.2.4 At each two month interval follow up visit out to 2 years all six prespecified cognitive test variables will be assessed. The pattern of cognitive change in memory, executive function, and processing speed will be assessed at each time point. The composite cognitive function

score will be determined by averaging standardized Z-scores from all pre-specified cognitive test variables (5 out of 6 are required to calculate a composite score).

- 10.2.5 MRI imaging including diffusion weighted images (DWI) and reconstructed apparent diffusion coefficient (ADC) maps will be analyzed for differences between pre- and post-treatment scans. They will also be analyzed for differences between the two treatment modalities.
- 10.2.6 Diffusion tensor imaging (DTI) will be analyzed for correlation to the cognitive changes and for differences between the two treatment modalities.
- 10.2.7 Pre-treatment factors of RPA class and MMSE will be assessed for predictive determination of local and distant control and cognitive outcome in each treatment arm.
- 10.2.8 Assessment will be made for correlation between location of primary lesion, total volume of intracranial disease, and cognitive outcome for each of the treatment arms.
- 10.2.9 The relationship between MGMT promoter methylation status and cognitive and local control outcomes will be assessed.
- 10.2.10 Post treatment side effects will be recorded at each follow up visit out to two years. Toxicity will be recorded according the Common Terminology Criteria for Adverse Events v4.0.3 for Nervous System Disorders. Only grade 3 and above toxicity that is directly related to therapy will be required to be documented. Pretreatment symptoms should not be considered as toxicity related to the treatment and are not required to be documented unless the symptoms worsen as a result of therapy.
- 10.2.11 Dosimetric parameters such as dose to the hippocampus will be analyzed for relationship with cognitive and local control outcomes.
- 10.3 Evaluation of correlative markers
 - 10.3.1 Genetic markers: DNA will be extracted within the first five fractions of treatment in the laboratory of the Study Chair. Apo E (i.e., Apo E2, Apo E3, and Apo E4) genes will be analyzed for single nucleotide polymorphisms (SNPs) either by Taqman or direct sequencing.

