We will use descriptive statistics to summarize by treatment arm the quality of life data at each assessment time. We will also use boxplots to summarize the quality of life data by treatment arm at each assessment time. We will model the quality of life data using mixed effects regression methods with repeated measures. The model will include treatment arm, selected dosimetric parameters, baseline cognitive function, location of the primary tumor (left vs. right hemisphere, if bilateral disease is present, location will be determined by the hemisphere with highest burden of disease), and the stratification factors used at randomization as fixed effects and patient as a random effect. We will similarly analyze the cognitive tests. For nearly all the prior mentioned analyses we will also plan to conduct an as-treated analysis.

We will tabulate by treatment arm the adverse events by grade and relationship to treatment.

We will use logistic regression methods to model the logit of the probability of neurocognitive decline as function of ApoE (i.e., Apo E2, Apo E3, Apo E4) genotyping, inflammatory markers (i.e., IL-1, IL-6, TNF- α), and hormone growth factors (i.e., glucocorticoids, gonadal steroids, growth hormone, human chorionic gonadotrpin, insulin-like growth factor-1, neuronal growth factor).

Determination of MCP class will be determined by RPA analysis using results of MGMT, *IDH1*, G-CIMP, and mRNA assays as well as RTOG RPA class. We will use descriptive statistics to report class distributions overall and by treatment arm. Survival by classes will be visualized on Kaplan/Meier plots, compared by the logrank test. The Cox proportional hazards regression will be used to model MCP classification, adjusting for treatment arm and stratification factors.

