13.0 Data and Protocol Management

13.1 To ensure protocol compliance, the principal investigator, treating radiation oncologist, study neuroradiologist and research nurse will review the patient data and MRI films prior to randomization. All required pretreatment data

should be available before a decision to enroll the patient on the protocol is made.

- 13.2 All data with the exception of the neuropsychological data will be collected by the research nurse in charge of the protocol. This includes pretreatment, treatment, and post treatment data. The neuropsychological data will be collected by members of the Section of Neuropsychology. [name] will maintain a study specific database containing the cognitive outcomes. The medical and neuropsychological databases will be integrated by the study statistician at the time of analysis and/or to prepare for MDACC DSMB review. The study chairman will act as the final arbitrator of all study parameters should a difference of opinion exist. Patients who meet eligibility criteria will be registered in CORe.
- 13.3 De-identified DICOM images and matched clinical variables will be shared with [name], PhD, University of Texas at Austin, Biomedical Engineering, TX, US; using secured M.D. Anderson Box cloud. The purpose of this collaboration is to spearhead an effort to leverage advanced imaging modalities, including multi-parametric and functional MRI to identify clinically applicable non-invasive means of characterizing radiation-induced normal brain injury and subsequent prediction of patterns of cognitive side effects.
- 13.4 De-identified DICOM images and matched clinical variables will be shared with [name], PhD, University of Michigan, Department of Computational Medicine & Bioinformatics; using secured M.D. Anderson Box cloud. The purpose of this collaboration is to spearhead an effort to leverage advanced imaging modalities, including longitudinal multi-parametric and functional MRI to identify clinically applicable non-invasive means of characterizing patterns of tumor response to radiation treatment.

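### The minimum recording rule for toxicity admits only grade 3+ events judged related to therapy, so attribution filters the between-arm safety comparison and part of the planned table has no required data

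*Combined protocol and SAP*

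**What the plan says.** Four places in the combined protocol and SAP bear on this.

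- **Objective 3.2.10**, a secondary objective: "To document and descriptively compare post-treatment adverse side effects between the two treatment arms".
- **Section 10.2.10**, the collection rule. It opens without any limit on grade or cause: "Post treatment side effects will be recorded at each follow up visit out to two years". It then fixes the scale: "Toxicity will be recorded according the Common Terminology Criteria for Adverse Events v4.0.3 for Nervous System Disorders". Next it sets the minimum: "Only grade 3 and above toxicity that is directly related to therapy will be required to be documented". Last, it says that symptoms present before treatment "are not required to be documented unless the symptoms worsen as a result of therapy".
- **Section 12.4**, the analysis: "We will tabulate by treatment arm the adverse events by grade and relationship to treatment". It defines no relationship categories and attaches no test.
- **Section 13.2**, the data collector: "All data with the exception of the neuropsychological data will be collected by the research nurse in charge of the protocol".

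On knowledge of the arm, section 7.2 states: "Following randomization, insurance pre-authorization will be obtained for the specified treatment modality". Sections 7.4 and 7.5 describe different planning systems and delivery machines for the two arms. The documents mention no masking, no criteria for relatedness and no adjudicator. Section 14 adds reporting of adverse treatment reactions to the IRB and annual DSMB review, but no rule to collect events regardless of cause.

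**The concern.** Relatedness is a judgement, and here it decides whether an event has to enter the dataset at all. It would do less harm as a label on an event already recorded. A between-arm comparison built on such data reflects both toxicity and attribution practice.

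The documents themselves show that attribution is difficult in this disease. Section 10.1.1 notes that progression often causes cognitive decline. Section 10.2.1.3 warns of pseudo-progression and asks the assessor to separate tumour-related deterioration from complications of therapy. Section 14.1 names swelling, oedema, necrosis and neurological decline as known risks of radiation. Every patient is also due to receive temozolomide (6.10), and 10.2.10 does not say whether therapy means radiation, drug or both.

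The protocol expects IMPT to do better on cognition (section 4.0) and describes proton toxicity as low (section 1.0). An assessor who knows the arm could therefore attribute similar events differently. At stake is the reading of objective 3.2.10, and whether the 12.4 table can be filled in evenly.

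**Working it through.** The plan gives no adverse-event rate, attribution probability or safety sample size, so there is no safety figure to reproduce. The main check is textual, and the arithmetic is an illustration only.

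**Step 1. Set the 12.4 table against the 10.2.10 minimum.**

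| Part of the 12.4 table | Required by 10.2.10? |
|---|---|
| Grade 3+, related | Yes (nervous-system terms) |
| Grade 3+, unrelated | No |
| Grade 1-2, any relationship | No |
| Pretreatment symptom that worsens, not as a result of therapy | No |

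The opening sentence of 10.2.10 could be read as covering every row, but the later sentence beginning with 'Only' narrows what must be documented. No other section restores the missing rows.

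**Step 2. Ask whether the arm is known when relatedness is judged.** The documents do not say who makes the judgement. They describe no masking, and the arm is evident from the insurance step (7.2) and the equipment (7.4, 7.5). Knowledge of the arm is therefore an inference, though a strong one.

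**Step 3. Illustrate what the filter can do.** The formula is

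recorded rate = true any-cause grade 3+ rate × probability that an event is judged related.

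The true rate is assumed to be 20% in both arms, so there is no real difference.

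| Attribution IMRT / IMPT | Recorded IMRT | Recorded IMPT | Ratio IMPT/IMRT |
|---|---|---|---|
| 60% / 40% | 0.20 × 0.60 = 12% | 0.20 × 0.40 = 8% | 0.67 |
| 50% / 50% | 0.20 × 0.50 = 10% | 0.20 × 0.50 = 10% | 1.00 |
| 40% / 60% | 0.20 × 0.40 = 8% | 0.20 × 0.60 = 12% | 1.50 |

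When the true rate is equal in both arms it cancels from the ratio. At 60% / 40%, a true rate of 10% gives 6% vs 4% and a true rate of 40% gives 24% vs 16%; the ratio is 0.67 each time.

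**Step 4. Convert to patients.** Section 12.2 targets 90 enrolled, or 90 / 2 = 45 per arm. The first row then gives 45 × 0.12 = 5.4 against 45 × 0.08 = 3.6 patients, a gap of 1.8. With the 30 evaluable patients per arm it is 3.6 against 2.4.

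**Step 5. Check that a real difference can also be hidden.** Assume true rates of 30% (IMRT) and 20% (IMPT), a ratio of 0.67. With attribution of 50% and 70%, the recorded rates are 0.30 × 0.50 = 15% and 0.20 × 0.70 = 14%, a ratio of 0.93.

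**The case against.** The best defence has five parts.

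1. **The rule is a floor.** It does not forbid wider recording, and the opening sentence of 10.2.10 points towards it. This is true, but recording beyond the floor would be voluntary and could be uneven between arms, so the two sentences still need reconciling.
2. **A reader might infer that the 12.4 table cannot be built.** The documents do not support that. Relationship categories are undefined, so the column could grade the strength of relatedness or split radiation from drug, and a table of related events by arm and by grade from 3 upwards is feasible. What is missing is required data for an unrelated category and for grades 1-2.
3. **Other records catch some of these events.** Neurological deterioration with grade III or worse toxicity counts towards local failure in 10.2.1.5, with no relatedness condition. Deterioration attributed to tumour counts as progression in 10.2.1.3. Visits, steroid use and unscheduled follow-up are recorded under section 9, and symptom and quality-of-life scores under 10.2.3. So events judged unrelated are not wholly lost, but none of this amounts to an all-cause adverse-event record.
4. **Bias is not demonstrated.** A reader might infer that unblinded staff demonstrably favour IMPT, or that the DSMB will see only filtered data. The documents do not name who judges relatedness, do not call the trial open-label, give no sign of the direction of any difference, and do not limit DSMB safety analyses to the 10.2.10 subset.
5. **All-cause counts have their own weakness.** In glioblastoma they will include tumour progression and could dilute a treatment signal. This stands, and it is a reason not to make the all-cause table the sole or main comparison.

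**Conclusion.** The point holds as an inconsistency between the collection rule and its stated use, together with an avoidable risk of bias. Section 10.2.10 lets a relatedness judgement determine which grade 3+ nervous-system events must be recorded, while 3.2.10 and 12.4 need data that this minimum does not secure.

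That the judgement is made with the arm known is inferred from the absence of any masking and from the visibly different treatments. That attribution would differ by arm is a possibility only. The size and direction of any bias cannot be derived from the documents. The ratios of 0.67, 1.00 and 1.50 rest on assumed rates and show that the effect could run either way or be nil; even with equal attribution, the unrelated events go unrecorded.

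The consequence is limited. The comparison is secondary and descriptive, with no test or decision rule attached, and the primary endpoint is unaffected. It should still be corrected, because a related-only table can be derived from all-cause records but the reverse is impossible.

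**What to change.** **In 10.2.10**, require every grade 3+ CTCAE nervous-system event to be recorded regardless of attribution, with relationship (radiation, temozolomide, tumour, other) as a separate field. Apply the same principle to pretreatment symptoms that worsen to grade 3 or above. Reword the opening sentence so that it and the minimum rule state one requirement.

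**In 12.4**, show the all-cause and the related-only tables side by side by arm, and limit the grade rows to the grades that 10.2.10 requires.

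This would also support 10.2.1.5, which needs grade III or worse neurological events without a relatedness condition.

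**Cost.** The research nurse makes some additional entries at follow-up visits that already take place; no new visits or tests are needed. The number of entries cannot be estimated, because the documents give no event rate. The all-cause counts will include tumour-related events, which is why the related-only table should stay beside them.

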11.0 Criteria for Removal from the Study

- 11.1 Analysis will be by intention-to-treat and those patients who withdraw from the study after randomization, but prior to receiving treatment will be tracked to ensure there is no bias introduced into the study.
- 11.2 Patients who do not complete the assigned treatment will be recorded and followed. These patients can be treated by best medical therapy as per the judgment of the treating physicians.

12.0 Statistical Considerations

- 12.1 Randomization procedure: A stratified block randomization procedure will be used. Randomization will be performed using CORe. The randomization strata are as defined above in section 7.0, and the block size will be 6. Patients who withdraw from the study after randomization, but prior to receiving treatment will be considered a cancel and replaced.
- 12.2 Sample size: With IMRT the cognitive function failure rate at 4 months is 45%, based off of comparative analyses of the cognitive failure rate of RTOG 0614 and compared to the cognitive impairment seen on RTOG 0525; we hope to demonstrate that IMPT can achieve a cognitive function failure rate at 4 months of only 30%. We assume the time to cognitive failure in each treatment arm follows an exponential distribution. A cognitive failure rate of 45% at 4 months then implies a median time to cognitive failure of 4.6 months, while a cognitive failure rate of 30% at 4 months implies a median time to cognitive failure to cognitive failure of 7.8 months.

We will use a 1-sided significance level of 0.20 as suggested by Rubinstein et al. [51]for phase II screening trials. We expect to enroll 2 patients per month, and we will randomize 60 evaluable patients (30 to each treatment arm). We will have 80% power to detect an improvement in cognitive failure at 4 months from 45% in the IMRT arm to 30% in the IMPT arm. We expect to observe 43 events, and the analysis will be performed once we have observed these events. We define evaluable patients as those who have received the assigned treatment *and* completed baseline and at least one follow-up neurocognitive testing. We expect we will need an over accrual of 33% to account for those patients not evaluable. Therefore the target total enrollment sample size is 90 patients to accrue a total of 60 evaluable patients. We expect to observe 43 events, and we expect the trial to take 41 months to observe these events.

- 12.3 Primary Analysis: The analysis will be performed on the intention-to-treat principle. Considering those patients who are not evaluable as treatment failures. We will use the methods of Gooley et al. [52]to estimate the cumulative incidence of cognitive failure in each treatment arm, considering progressive disease and death before cognitive failure as competing events. We will estimate the cumulative incidence of cognitive failure at 4 months with 95% confidence intervals. We will use the methods of Fine and Gray [53]to test for a difference between treatment arms with respect to the cumulative incidence of cognitive failure, considering progressive disease and death before and death before and death before cognitive failure as competing events. We will use the methods of Fine and Gray [53]to test for a difference between treatment arms with respect to the cumulative incidence of cognitive failure, considering progressive disease and death before cognitive failure as competing events. Our model will include treatment arm and the stratification factors used at randomization.
- 12.4 Secondary Analysis:

We will repeat the primary analysis on only those patients considered evaluable. All the secondary analyses described below will be performed using all patients as well as using only evaluable patients. We will estimate the cumulative incidence of local failure using the methods of Gooley et al. considering death as a competing event. We will model the time to local failure using the methods of Fine and Gray to test for differences between treatment arms, considering death as a competing event. Our model will include treatment arm and the stratification factors used at randomization, as well as selected dosimetric parameters. We will similarly analyze time to distant failure.

We will use the product limit estimator of Kaplan and Meier [54] to estimate overall survival stratified by treatment arm. We will also use Cox proportional hazards regression [55] to model overall survival as a function of treatment arm and the stratification factors used at randomization.

We will use descriptive statistics to summarize by treatment arm the quality of life data at each assessment time. We will also use boxplots to summarize the quality of life data by treatment arm at each assessment time. We will model the quality of life data using mixed effects regression methods with repeated measures. The model will include treatment arm, selected dosimetric parameters, baseline cognitive function, location of the primary tumor (left vs. right hemisphere, if bilateral disease is present, location will be determined by the hemisphere with highest burden of disease), and the stratification factors used at randomization as fixed effects and patient as a random effect. We will similarly analyze the cognitive tests. For nearly all the prior mentioned analyses we will also plan to conduct an as-treated analysis.

We will tabulate by treatment arm the adverse events by grade and relationship to treatment.

We will use logistic regression methods to model the logit of the probability of neurocognitive decline as function of ApoE (i.e., Apo E2, Apo E3, Apo E4) genotyping, inflammatory markers (i.e., IL-1, IL-6, TNF- α), and hormone growth factors (i.e., glucocorticoids, gonadal steroids, growth hormone, human chorionic gonadotrpin, insulin-like growth factor-1, neuronal growth factor).

Determination of MCP class will be determined by RPA analysis using results of MGMT, *IDH1*, G-CIMP, and mRNA assays as well as RTOG RPA class. We will use descriptive statistics to report class distributions overall and by treatment arm. Survival by classes will be visualized on Kaplan/Meier plots, compared by the logrank test. The Cox proportional hazards regression will be used to model MCP classification, adjusting for treatment arm and stratification factors.

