Decreased dosage to critical normal brain tissues has been suggested to translate into improved cognitive function. Merchant et al. compared dose characteristics for four types of common childhood brain tumors treated using conformal protons versus photons and in dosevolume modeling systems found that proton plans resulted in better cognitive outcomes. Specific advantages included decreased IQ loss, less cochlea damage, and decreased endocrine effects[10]. The study of long term benefit of proton therapy in pediatric patients will require years of follow up but the preliminary results are encouraging. Similarly Arvold et al. modeled doses for protons versus photons in the treatment of benign meningiomas. They showed that protons could decrease the risk of radiation associated secondary malignancies by half and that lower doses to critical structures supporting cognitive functions such as memory including the temporal lobe and hippocampus could be achieved with proton plans [21].

While the theoretical dosimetric advantages of proton plans are intriguing we do not have randomized data comparing cognitive outcomes in glioblastoma patients treated with these two modalities. We hypothesize that IMPT will result in improved cognitive outcomes. In this trial we propose to address this question by prospectively randomizing patients with glioblastoma to treatment with IMRT versus IMPT. Patients will be stratified by RPA class, Mini Mental Status Examination score (21-26 vs. 27-30)[17], and age (less than 65 vs. 65 and older). These factors are known to have prognostic significance. The primary endpoint will be time to first cognitive failure on any of the following six cognitive test variables: HVLT-R Total Recall, HVLT-R Delayed Recall, HVLT-R Delayed Recognition, COWA, and TMT A or B. Secondary endpoints will include local control and overall survival outcomes as well as quality of life. Addressing this question in a prospective randomized fashion can be accomplished at MDACC given the high volume of cancer patients with glioblastoma treated at our center.

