6.0 Patient Eligibility

Inclusion Criteria:

- 6.1 All patients must have histological proof of glioblastoma or gliosarcoma (WHO Grade IV) adapted RPA class III, IV, or V.
- 6.2 All patients must be ≥ 18 years of age.
- 6.3 All patients must sign informed consent verifying that they are aware of the investigational nature of this study in keeping with the rules and policies of M.D. Anderson Cancer Center. The only acceptable consent form is the one approved by M.D. Anderson IRB.
- 6.4 All patients must have a baseline Mini Mental Status Examination score \geq 21.
- 6.5 All patients must have a KPS \geq 70.
- 6.6 All patients must be eligible to have either IMRT or IMPT as determined by the study radiation oncologist.
- 6.7 All patients must be able to undergo MRI with and without contrast with a glomerular filtration rate (eGFR) greater than or equal to 30 mg/min/1.72 m².
- 6.8 All patients must have adequate liver, renal, and hematologic function within 14 days of registration as defined by Aspartate Amino Transferase (AST)/Alanine Amino Transferase (ALT)/Alkaline Phosphatase < 3 times normal, creatinine \leq 1.7 mg/dl, BUN \leq 35mg/dl, absolute neutrophil count \geq 1,800 cells/mm³, Hemoglobin \geq 10 g/dl, and platelet count > 100,000.
- 6.9 All patients must be able to adequately read, write and speak to participate in the cognitive and quality of life assessments. However mild to moderate deficits in these functions due to tumor are allowed.

Exclusion Criteria:

- 6.10 Patients will be excluded if they are not planning to receive concurrent temozolomide.
- 6.11 Patients will be excluded if they have had prior radiation to the brain.
- 6.12 Patients will be excluded if they have had prior surgical resection of brain for other brain tumors.
- 6.13 Patients will be excluded if they are pregnant as assessed by serum b-HCG. A serum b-HCG test will be performed no greater than 14 days prior to study registration for women of childbearing potential.
- 6.14 Patients with gliomatosis will be excluded.
- 6.15 Patients with Glialdel (BCNU) implanted wafers will be excluded.
- 6.16 Patients weighing greater than 136 kilograms will be excluded.

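### The single fixed block size of 6 stated in section 12.1 lets a team that sees earlier assignments deduce about 18 of the 90 planned assignments

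*Combined protocol and SAP*

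**What the plan says.** Section 12.1 states: "A stratified block randomization procedure will be used". It runs through CORe, and "the block size will be 6". No variation in block size is described, and no limit on who may know it.

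Section 7.1 sets the ratio and the strata: "Eligible patients will be randomized in equal numbers to each treatment arm using CORe", stratified by "RPA class (III or IV vs. V"), "Mini Mental Status Examination score (21-26 vs. 27-30") and "Age (less than 65 vs. 65 or older"). Site is not a factor.

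Four other places matter:

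- **One institution.** Section 4.0 says that the question "can be accomplished at MDACC given the high volume of cancer patients with glioblastoma treated at our center".
- **Arm known at once.** Under section 7.2, insurance approval for the assigned modality is sought after randomization. Sections 7.4 and 7.5 give the arms different planning systems and machines. No blinding is described.
- **Judgement at entry.** Criterion 6.6 reads: "All patients must be eligible to have either IMRT or IMPT as determined by the study radiation oncologist". Section 13.1 has the principal investigator, treating radiation oncologist, neuroradiologist and research nurse review each candidate's data before randomization.
- **Cancels.** Under section 12.1, a patient who withdraws between randomization and treatment is a cancel and is replaced. Section 7.2 removes patients whose insurer will not pay for the assigned arm.

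The documents do not use the terms open-label or single-centre. Both are inferences from these sections.

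**The concern.** A central system hides the allocation list. It cannot hide an assignment that follows from a known block size and known earlier assignments: once three patients in a block of six have gone to one arm, the rest of that block must go to the other.

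The ingredients for that deduction are all present. The size is printed in the protocol, one team can see every assignment, and RPA class, MMSE and age are known before registration, so the team can tell which sequence a candidate would join. Entry also involves clinical judgement. A clinician who knows the next arm could, even without intending to, enter, defer or decline a candidate accordingly.

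At stake is comparability of the arms on cognitive prognosis. The primary model in section 12.3 includes the stratification factors, so selection on those is largely dealt with. Selection within a stratum on something not measured would stay in the treatment estimate.

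**Working it through.** The documents give no figure for predictability, so there is none to reproduce.

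**Inputs.** Block size 6 (12.1); 1:1 allocation, so 3 + 3 per block (7.1); 2 × 2 × 2 = 8 strata (7.1); 90 patients enrolled (12.2). The stratum mix is not given and is assumed below. The observer is assumed to know all earlier assignments in the stratum, cancels included.

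**Step 1: one completed block.** There are C(6,3) = 20 equally likely blocks. The next assignment is certain when one arm already has its three patients.

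| Position | Chance that the assignment is certain |
|---|---|
| 1, 2, 3 | 0 |
| 4 | 2/20 = 0.1 |
| 5 | 8/20 = 0.4 |
| 6 | 1.0 |

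The sum is 1.5 per block, and 1.5/6 = 25%. In general a fixed block of 2m gives a share of 1/(m + 1): 33.3% for size 4, 25% for size 6, 20% for size 8. Another single fixed size would therefore not solve the problem.

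**Step 2: best guess in a completed block.** Guessing the arm that is behind is right with probability 0.5, 0.6, 0.6, 0.7, 0.7 and 1.0 at positions 1 to 6. The mean is 4.1/6 = 68.3%, against 50% by chance.

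**Step 3: the planned trial.** Eight strata share 90 patients, 90/8 = 11.25 each on average, so most strata end part-way through a block, where fewer assignments are certain. A stratum of 11 has one full block and five positions of the next: 1.5 + 0.5 = 2.0 certain, and 2.0/11 = 18.2%. Simulating 90 patients over the strata gives:

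| Assumed stratum mix | Certain, of 90 | Share |
|---|---|---|
| 8 equal strata | 18.3 | 20.3% |
| 70/30 on each factor | 18.3 | 20.3% |
| 80/20 on each factor | 18.6 | 20.6% |
| Only 6 strata fill | 19.4 | 21.5% |
| Only 4 strata fill | 20.4 | 22.7% |

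**Step 4: varying block sizes.** Here the observer knows the possible sizes but not their order, and updates exactly after each assignment (simulation, 90 patients, 8 strata).

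| Block sizes | Certain | Best guess right |
|---|---|---|
| 6 fixed | about 20% | about 66% |
| 4 and 6 at random | about 6% | about 67% |
| 4, 6 and 8 at random | about 2% | about 66% |

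As counts, about 18 certain assignments become about 5 (0.06 × 90) or about 2 (0.02 × 90). The best-guess rate hardly moves.

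**The case against.** Fixed permuted blocks run through an institutional system are a recognised method, and nothing in the plan is contradictory or unworkable. The case for leaving it alone has four parts.

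- **Varying blocks do not lower the best-guess rate.** This stands. A clinician can act on a likely assignment as well as a certain one, and with sizes 4 and 6 the rate is, if anything, slightly higher. The gain is the removal of certainty. Withholding the sizes may help further, but that benefit is not quantified here.
- **The observer is a worst case.** Partly stands. Someone must follow eight interleaved sequences. At the 2 patients per month in section 12.2, each gains a patient about every four months on average (8/2). Whether a cancelled slot is reused is not stated, so an observer may lose the position in the block. But such slow accrual also makes a hand tally easy, and staff at one institution would see the cancellations.
- **Entry is constrained.** Partly stands. The joint review in section 13.1 limits one person's freedom to act. It does not conceal the assignment, and the reviewers are the people who can know the earlier ones.
- **No bias in the result is shown.** This stands. No effect on the hazard ratio, type I error or power has been estimated.

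A reader might infer that a quarter of all assignments in this trial are certain. That holds only for completed blocks; with 8 strata and 90 patients the expected share is nearer one fifth.

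**Conclusion.** The point holds as a cheap improvement. One disclosed, fixed block size makes 25% of assignments in each completed block certain to an observer who knows the earlier ones in the stratum. That is about 18 of the planned 90 (20%), or up to about 20 if only four strata fill. The figures assume full knowledge of earlier assignments and an assumed stratum mix. They also rest on the inference that the trial is open-label and single-centre, and cancelled slots could blur the count.

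A reader might infer that enrolment was selective, or that the treatment comparison is biased. The documents do not support that: they show an opportunity, not its use. Nor would selection be wholly beyond repair, since RPA class, MMSE and age are stratified and modelled. The residual concern is selection on unmeasured prognosis within strata.

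**What to change.** 1. Set CORe to draw block sizes at random, for example from 4, 6 and 8, which cuts certainty further than 4 and 6 alone.
2. Remove the block size from section 12.1, saying only that sizes vary and are not disclosed, and hold them in a document open to the statistician alone.
3. If enrolment has begun, apply this to the remaining blocks.
4. State whether a cancelled patient's slot is reused.

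The cost is a system setting and a small text change. Imbalance within a stratum could be slightly greater: at most 4 patients part-way through a block of 8, against 3 in a block of 6. The protocol team should not expect the change to make assignments hard to guess; it removes most of those that can be known for certain.
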